1.7 Phase 3: Staff population

Phase 3 of the study aims to evaluate staff's views about how the novel use of multi-parametric and micro ultrasound impacts on their work, and their expectations about whether it could become a routine part of their clinical practice.

1.7.1 Cohort

Phase 3 participants are invited from the staff population. Sonographers and radiologists involved in the current prostate cancer pathway will be invited to participate in the study.

1.7.2 Data collection tool

Normalization Process Theory (NPT) provides a framework for understanding how a new intervention becomes part of normal practice. A survey aligned with NPT will be used to develop an understanding of the complexity of the work involved in the implementation of using ultrasound within prostate cancer diagnosis and assessment. The survey will be used at the beginning of the study and again at between 6 - 12 months' post commencement to evaluate if perceptions have changed over time. NPT will be used to better understand healthcare practitioners feel about the implantation of new and complex techniques and technology.

1.7.2.1 NPT components

Qualitative data, collection via the survey from participants in phase 3, will be gathered to better understand the following:

- When they use and interpret / score the new technology how familiar does it feel?
- Do they feel that the new technology and interpretation is currently a normal part of their work?
- Do you feel that the new technology and interpretation will become a normal part of their work?

1.7.2.2 NPT domains

The survey will investigate the four domains of NPT. It will investigate the ways that participants make sense of the work of implementing and integrating multi-parametric and micro ultrasound into practice (coherence); how they engage with it (cognitive participation); enact it (collective action); and appraise its effects (reflexive monitoring). This phase of the study will evaluate any differences between different grades of staff using ultrasound in this study and between professional groups involved. Skill mix is an important consideration when implementing new techniques or interventions to ensure that these can be successfully integrated into real world clinical practice.

1.7.3 New technology impact assessment

Phase 3 will investigate the impact that differing professional groups may have on developing and implementing new technologies although the small sample size will preclude any quantitative data analysis. A narrative review will be provided.

1.7.4 Phase 3 sample

Participants for phase 3 will be invited from the whole cohort of professionals who work within the radiology team currently involved with prostate imaging within the Hull University Teaching Hospital NHS Trust. This cohort of professionals includes urology specialised radiologists and sonographers who are involved with the production and interpretation of prostate imaging, and will also include urology consultants and urology registrars who are involved with reading and decision making from prostate imaging at multi-disciplinary team meetings. Sonographers in this cohort are radiographers who have undertaken Masters level post graduate training in medical ultrasound and specialised in specific prostate imaging. Relevant staff employed within this service will be given study information leaflets and invited to join the study. The phase 3 cohort will be a maximum of 12 staff members from varying professions.

1.7.5 Conflicts of interest

Whilst it is important to maintain anonymity within this group, this will be difficult to maintain as the numbers of staff within each professional group is small. Data analysis will only be undertaken by the lead researcher and all results will be shared sensitively with consideration that confidentiality will be maintained at all times. Identifiable data will not be published or shared. The lead researcher

who will be involved in the acquisition and scoring of the multi-parametric ultrasound images but will not complete a phase 3 survey to prevent bias. However, the lead researcher will complete a survey independent of the study at implementation and at 12 months and use this to inform their reflection of the study and personal development within their clinical role.

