1.7.6 Lead researcher considerations

The lead researcher is a key player in the small clinical team and integral in ensuring NHS service delivery can be maintained. The lead researcher is also the clinical lead sonographer for the ultrasound service within the trust. It is recognised that this may cause unnecessary conflict and bias. To avoid this, and to minimise the risk of coercion consent for participation within phase 3 of the study will be obtained by the recognised PhD clinical supervisor, [name], Consultant Urologist, who is overseeing the clinical aspect of the study with the lead researcher. This potential conflict is an acknowledged risk and will be managed by open communication and by ensuring participants have the option to withdraw consent to participate at any time with no adverse effects.

1.7.7 Inclusion criteria for phase 3

- Health care practitioner working as a radiologist or sonographer and employed within radiology of Hull University Teaching Hospitals NHS Trust
- Hold a recognised qualification awarded by the Royal College of Radiologists or a recognised post graduate ultrasound qualification undertaken at a CASE approved higher education institute
- Registered with a statutory regulator such as the GMC, NMC or HCPC
- Participates in the current radiology prostate cancer assessment care pathway
- Able to provide informed consent to the study

1.7.8 Exclusion criteria for phase 3

- Health care practitioners not employed in Hull University Teaching Hospitals NHS Trust
- Sonographers or radiologists not directly participating in the current radiology prostate cancer assessment care pathway
- Sonographers or radiologists who do not hold relevant qualifications listed within the inclusion criteria
- Sonographers or radiologists who do not hold relevant statutory registration
- Sonographers or radiologists who do not consent to participate in the study

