1.7.9 Phase 3 data collection

The survey is designed using the tool related to the normalisation process theory. The Normalisation MeASURE Development (NoMAD) tool is a questionnaire of survey items used to assess the

implementation processes of this new technology. A paper copy of the survey questions is provided in Appendix 8. The survey will be created within the JISC (Joint Information Systems Committee) online survey tool and distributed anonymously to all participants; it is acknowledged that anonymity is difficult to maintain due to the small cohort of staff and the wide variety of individual roles.

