1.10.3.1 Risk

There is minimal risk to health care practitioners participating in phase 3 of the study. There is an established group of sonographers and radiologists providing the radiology prostate cancer assessment care pathway. There is a risk to the study of attrition of participants due to the age

demographics of the available workforce and staff relocating. There is also a risk of conflict between professional groups as knowledge and skills develop. This will be mitigated by regular communication with the study groups, led by the lead researcher and supported by the academic supervisory team as a non-involved third party. The greatest risk however is due to the lead researcher having a pivotal leadership role within the team and crucial to normal service delivery. There is a risk of unintentional bias from participants either feeling they should participate or feeling the need to please. These risks will be mitigated by open and honest communication with all team members upon recruitment and during the study.

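### The lead researcher, who leads the sonographers' service, is the only person assigned to analyse a hard-to-anonymise staff survey, and the protocol contradicts itself on who may answer it and who takes consent

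*Protocol*

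**What the plan says.** Section 1.7.5 gives the analysis to one person, as part of its confidentiality arrangements: "Data analysis will only be undertaken by the lead researcher and all results will be shared sensitively". Section 1.7.6 adds that "The lead researcher is also the clinical lead sonographer for the ultrasound service within the trust". Section 1.7.5 also says that the lead researcher takes part in acquiring and scoring the images but "will not complete a phase 3 survey to prevent bias"; a survey that the lead researcher completes separately is kept outside the study.

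On the size of the group, section 1.7.4 states: "The phase 3 cohort will be a maximum of 12 staff members from varying professions". On anonymity, section 1.7.9 has the survey sent anonymously through an online tool, but "it is acknowledged that anonymity is difficult to maintain due to the small cohort of staff". Section 1.10.3.1 names the lead researcher's position in the team as the greatest risk of this phase and continues: "There is a risk of unintentional bias from participants either feeling they should participate or feeling the need to please".

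On who may answer, section 1.7.4 says the cohort "will also include urology consultants and urology registrars who are involved with reading and decision making from prostate imaging", and Appendix 8 lists consultant urologist and urology registrar among the professional backgrounds. The inclusion criteria in 1.7.7 admit only radiologists and sonographers employed within radiology.

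**The concern.** Phase 3 asks staff whether the new ultrasound technique can become routine in their work. Its value rests on candid answers. The protocol identifies a bias, attributes it to the lead researcher's position, and then makes that same person the sole analyst of the answers. No other holder of the survey data is named.

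There is a second, smaller gap. The lead researcher is kept out of the survey to prevent bias. The same reasoning applies to any other investigator on the project, yet nothing is said about them.

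Candour lost at the baseline survey cannot be restored afterwards. Section 1.7.3 rules out quantitative analysis because the sample is small, so no later adjustment is available. The route the answers take has to be settled before the first survey goes out.

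**Working it through.** No design figure needs reproducing: 12 is a cap, not the result of a formula. The check is a comparison of sections plus two lines of arithmetic.

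**1. Does any stated safeguard change who sees the answers?**

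| Safeguard | Section | Effect on who sees the answers |
|---|---|---|
| Anonymous online distribution | 1.7.9 | Helps, but the same sentence concedes its limits |
| Open communication | 1.7.6, 1.10.3.1 | None |
| Right to withdraw without adverse effects | 1.7.6 | None |
| Supervision of phase 3 data collection and analysis | 1.14 | None stated: no task or second analyst is named |
| Academic supervisors as an outside party | 1.10.3.1 | None: assigned to conflict between professional groups, not to survey data |
| Opt-out on professional background | Appendix 8 | Partial: covers that field; the role question, as shown, lists three roles and no opt-out |
| Consent taken by the clinical supervisor | 1.7.6 | None, and contradicted by 1.9.3, where the lead researcher obtains written consent |

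**2. How small are the groups?** Inputs: at most 12 respondents (1.7.4) and five named professional backgrounds (Appendix 8).

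- Average per profession: 12 / 5 = 2.4.
- If every profession had at least 3 respondents, the total would be at least 5 × 3 = 15, which exceeds 12. So at least one profession has two or fewer.

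An analyst who works in the team could therefore recognise some respondents from profession alone, unless they use the opt-out. This agrees with what the protocol concedes.

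**3. Can a research-team member answer?** The research team listed at the front of the protocol includes a consultant urologist of the trust.

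- Sections that admit a consultant urologist: 1.7.4 and Appendix 8.
- Sections that do not: 1.7.1, which invites sonographers and radiologists, and 1.7.7.
- Bar by reason of research-team membership: stated in 1.7.5 for the lead researcher only.

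Such an answer is thus possible under one set of sections and excluded under the other. If one were given, its weight would be at least 1 / 12 = 8.3% of respondents, and more if fewer than 12 take part.

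**The case against.** The strongest reply is that the conflict is disclosed, that a doctoral researcher analysing their own data under supervision is normal, and that phase 3 is a frequency table and narrative serving one secondary objective. All of that stands. It limits the weight of the point, but it does not answer the question of who reads the raw answers.

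Four stronger readings are tempting and are not supported.

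- *Only the lead researcher is barred, so an investigator will answer.* Section 1.7.7, read literally, shuts out every urologist, and 1.7.8 bars staff not employed by the trust. No section says that the clinical supervisor intends to answer. What stands is that the lead researcher is the only team member expressly excluded and that the eligibility sections conflict.
- *All respondents answer to their own clinical lead.* The leadership role is documented for the ultrasound service. Nothing says it extends to radiologists, urologists or registrars, so the wish to please is best supported for sonographers.
- *The answers are as good as signed.* Distribution is anonymous and Appendix 8 lets a respondent withhold professional background. Any estimate of how many people are unique by profession and role needs an assumed staff mix and an assumed link between the two, which the protocol does not give.
- *The results will be favourable.* The protocol supports a risk, and the direction is plausible, but nothing in it proves either direction or size.

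A fair objection to one obvious remedy also stands. Merging professions into broad groups for the whole analysis would remove the comparison between grades and professional groups that 1.7.2.2 plans.

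**Conclusion.** The point holds in a limited form. A survey of at most 12 staff, conceded to be hard to keep anonymous, is to be analysed only by the person whose position the protocol names as the greatest phase 3 risk. None of the listed safeguards alters that, and the sections on consent (1.7.6 against 1.9.3) and on eligibility (1.7.4 and Appendix 8 against 1.7.1 and 1.7.7) contradict each other.

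The size of any bias cannot be computed. What can be said is that at least one of the five professions will have two or fewer respondents, and that one research-team answer would be at least 8.3% of the total. The first statement takes the five backgrounds in Appendix 8 as the grouping; the second applies only if such a person is admitted and answers.

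A reader might infer that the study's main findings are compromised. They are not on this ground: the imaging comparisons of phases 1 and 2 do not use the survey. The change should be made because it is cheap and must precede the baseline survey.

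**What to change.** In section 1.7.5:

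- **(a)** State that an existing academic supervisor outside the surveyed team holds the survey export and gives the lead researcher the item answers without the role and profession fields. The supervisor supplies the frequency tables by profession, which keeps the comparison planned in 1.7.2.2. Respondents are told this before the baseline survey. Because a table for a profession with one respondent still shows that person's answers, say in advance how such a group will be displayed.
- **(b)** State that no member of the research team completes a phase 3 survey.

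Elsewhere, reconcile 1.7.4 and Appendix 8 with 1.7.1 and 1.7.7 on who may answer, and 1.7.6 with 1.9.3 on who takes phase 3 consent.

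The cost is a few sentences, a short task for a supervisor already in place, possibly one fewer respondent, and less ability to link a single answer to a profession. The lead researcher remains the analyst of the item answers.

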1.7.6 Lead researcher considerations

The lead researcher is a key player in the small clinical team and integral in ensuring NHS service delivery can be maintained. The lead researcher is also the clinical lead sonographer for the ultrasound service within the trust. It is recognised that this may cause unnecessary conflict and bias. To avoid this, and to minimise the risk of coercion consent for participation within phase 3 of the study will be obtained by the recognised PhD clinical supervisor, [name], Consultant Urologist, who is overseeing the clinical aspect of the study with the lead researcher. This potential conflict is an acknowledged risk and will be managed by open communication and by ensuring participants have the option to withdraw consent to participate at any time with no adverse effects.

1.7.7 Inclusion criteria for phase 3

- Health care practitioner working as a radiologist or sonographer and employed within radiology of Hull University Teaching Hospitals NHS Trust
- Hold a recognised qualification awarded by the Royal College of Radiologists or a recognised post graduate ultrasound qualification undertaken at a CASE approved higher education institute
- Registered with a statutory regulator such as the GMC, NMC or HCPC
- Participates in the current radiology prostate cancer assessment care pathway
- Able to provide informed consent to the study

1.7.8 Exclusion criteria for phase 3

- Health care practitioners not employed in Hull University Teaching Hospitals NHS Trust
- Sonographers or radiologists not directly participating in the current radiology prostate cancer assessment care pathway
- Sonographers or radiologists who do not hold relevant qualifications listed within the inclusion criteria
- Sonographers or radiologists who do not hold relevant statutory registration
- Sonographers or radiologists who do not consent to participate in the study

1.7.9 Phase 3 data collection

The survey is designed using the tool related to the normalisation process theory. The Normalisation MeASURE Development (NoMAD) tool is a questionnaire of survey items used to assess the

implementation processes of this new technology. A paper copy of the survey questions is provided in Appendix 8. The survey will be created within the JISC (Joint Information Systems Committee) online survey tool and distributed anonymously to all participants; it is acknowledged that anonymity is difficult to maintain due to the small cohort of staff and the wide variety of individual roles.

1.7.10 Phase 3 participant and data confidentiality

Confidentiality will be maintained. The responses will be analysed in a simple tabular format summarising the frequency of responses to items which will indicate where participants are providing more positive or negative responses.

1.7.11 Data analysis

A narrative of the qualitative data collected will be produced to identify the main themes that may provide an opportunity for development or either technology or skill set of the participant as well as identifying the barriers to implementation.

1.8 Phase 4

A fourth phase of the study is planned. Once outcomes from the initial 3 phases of the study are known the lead researcher intends to participate in a national meeting where results will be presented and discussion held between the research team and other centres providing a diagnostic prostate cancer service. The lead researcher has experience of planning and organising national study events and has access to the British Medical Ultrasound (BMUS) Team who will facilitate. The event will be open to all centres providing a prostate service. Notes will be taken during the event to form a narrative of proposed service developments. Attendees at the event will be informed that the event is being undertaken as an outcome of the research study and will be invited to participate in discussions around the study findings and implications for future service delivery.

1.8.1 Inclusion criteria for phase 4

- Delegates attending the specific prostate imaging workshop organised through BMUS
- Able to provide informed consent to the study
- Delegates who are happy to participate in discussion but who do not want their own comments recorded. Reference is made to the Phase 4 consent to study sheet (ICF V2 03.11.2021)

1.8.2 Exclusion criteria for phase 4

- Delegates attending the study event who do not consent to participate in the study

- Delegates who register for the study event but fail to attend. Notes from face to face discussion only will be recorded in the interests of transparency for all participants

1.9 Consent

Written consent will be obtained from all participants in all three phases of the study.

1.9.1 Phase 1 consent

Phase 1 participants will be informed of the study at their initial clinic appointment with a nurse practitioner. A leaflet will be given to the men to read prior to attending for their pre-biopsy MRI examination. Once the MRI has been completed the men will be contacted by telephone and invited onto the study. Those that give verbal consent at that stage will be met by the lead researcher on the day of their routine prostate biopsy appointment and written consent will be obtained.

1.9.2 Phase 2 consent

All histology results post prostate biopsy are currently recorded in the hospital patient information system with the prostate biopsy record. These are discussed at the urology multi-disciplinary meeting and decision to treat or offer active surveillance made. Details of men moving onto AS will be communicated to the lead researcher by the MDT coordinator using a password protected internal hospital database. These men will be contacted by the lead researcher and invited onto phase 2 of the study.

The consent procedure, for both phase 1 and phase 2 of the study, will involve talking to the participant, explaining the aims of the research to them, explaining the aims and objectives of the study, and explain study procedures, and the possibility to withdraw from the study at any given moment without giving any justifications or explanations. The consent form will include permission to continue to use data already collected should a participant withdraw from the study.

Participants will only be included in the study if they are freely able to provide valid consent. Consent forms will discuss the issues related to continued participation in the study should the participant lose capacity and include permission for continuation of data analysis of data that has already been collected should the participant lose capacity to consent.

1.9.3 Phase 3 consent

Phase 3 participants will be invited into the study to both undertake multi-parametric ultrasound imaging, and to provide a retrospective score of the saved images. Phase 3 participants will also be required to undertake 2 surveys to provide their views of the new technology using the NoMAD

survey. The requirements of the study will be fully explained in a leaflet prior to a face to face discussion where written consent will be obtained by the lead researcher. Care will be taken to ensure there is no conflict between the lead researchers research role and her clinical role to prevent coercion of team members participating in the study

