1.5.12 Data assessment

The set of images and cine loops will be reviewed, in retrospect, by the assigned reviewers. The images and cine loop will be reviewed via a PACS workstation with monitor quality, and viewing conditions, as similar as possible to the ultrasound monitors and scan rooms. The save images will be scored using a 5-point scale, similar to the established PI-RADSV2 prostate reporting scoring system used to report MRI. This 5-point scale provides a score of the ultrasound appearance ranging from homogeneous and mid-grey (highly likely to be benign) through to heterogeneous and echo-poor (highly likely to be malignant). Any identified focal areas will be measured and the site documented dependent upon where in the gland the image was taken. Assessment of the presence of Colour flow Doppler will documented on a 3-point scale ranging from no colour Doppler signal evident to florid colour Doppler evident (signal fills the imaging sample box). The scoring system for the standard ultrasound and micro ultrasound images is provided in [Appendix 6](#) (standard) and [Appendix 7](#) (micro). Once reviewed, the scores submitted on the data collection forms will be uploaded onto the database by the lead researcher.

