1.5.13 Data collation

Once the reviewers scores have been uploaded onto the database, the lead researcher will review the clinical information taken as part of the standard care consultation. This will include the PSA level and documented DRE report. Both will be added to the database. The MRI report is undertaken

as part of the standard care pathway. The MRI PI-RADS score and documented site of abnormality will be recorded on the data base. The histology results of any prostate biopsies undertaken will also be reviewed and the histological Gleason score added to the database.

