1.5.14 Data analysis

Once the database is complete for each participant, the lead researcher will compare the:

- ultrasound scores
- ultrasound colour Doppler findings
- prostate volume size
- lesion size

The above criteria will be compared between both the standard and micro-US imaging, and then the standard and micro-US with both MRI and histology. An assessment of agreement will be undertaken to evaluate the concordance between the two reviewers of the same images (Ranganathan, Pramesh and Aggarwal 2017). The relationship between these pairs will be evaluated using Bland-Altman plots. Scores from the ultrasound reviews will also be evaluated to determine inter-and intra-operator agreement between the randomly allocated reviewers. The inter-rater reliability, both within and across subgroups of reviewers, will be assessed using the intra-class correlation coefficient or the Cohen weighted kappa test (de Raadt et al. 2021).

1.6 Study design and methodology – Phase 2

Men eligible for AS will be invited to participate in phase 2. A multi-parametric US examination will be undertaken as part of the AS monitoring regime. Men under AS have a prostate serum antigen (PSA) blood test and digital rectal examination every 6 months. A multi-parametric US examination will be undertaken at these appointments to minimise unnecessary health care interactions for the participants. The multi-parametric US examination will be performed blinded to the previous examinations and histology results. The images will be scored and then correlated with previous imaging scores and current PSA levels. Any changes will be indicated to the lead urologist and the patients will be offered MRI imaging to evaluate any changes using existing gold standard imaging.

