1.6.6 Participation and patient contact

Following consultation and treatment choice the eligible patients will be given an information leaflet about the study. The lead researcher will be informed of the patients who have been approached by the specialist nurse. The lead researcher will then contact the patient by telephone and invite them to participate in the study. The phase 2 recruitment pathway is provided in [appendix 3](#). Once verbal consent has been given, a mutually convenient appointment will be made and confirmed with an appointment letter.

The patient will attend for agreed appointment and a face to face consultation with the lead researcher will be undertaken to discuss the study and obtain written consent. The lead researcher will be blinded to the results of the MRI and any previous ultrasound image collection at this time to minimise undue coercion into the study, as in phase 1.

1.6.7 Image collection Phase 2

The [ultrasound examination](#) described and image collection for phase 2 is identical to that of [phase 1](#). The exception being that once the images have been collected and stored the patient will be free to leave; no further consultation, procedure or examination will be undertaken.

1.6.8 Data collection phase 2

The data collection of phase 2 is identical to that of [phase 1](#). Data collections forms utilised are attached in [Appendix 6](#) & [Appendix 7](#). The current standard and micro-ultrasound collected as part of phase 2 will be reviewed by two randomly allocated reviewers and scored as outlined above.

1.6.9 Data assessment phase 2

Once scored the documented criteria will be compared between both the standard and micro-US imaging collected during phase 2, and then compared with the previous standard and micro-US imaging [collected](#) during [phase 1](#).

1.6.10 Data analysis phase 2

The relationship between these pairs will be evaluated using Bland-Altman plots as per [phase 1](#). Scores from the ultrasound reviews will also be evaluated to determine inter-and intra-operator agreement between the randomly allocated reviewers. The phase 1 images and cine loop are the baseline data that all subsequent phase 2 examinations undertaken on that particular participant will be compared.

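### Phase 3 consent is assigned to two different people, and following section 1.9.3 removes the consent-taker chosen to limit coercion; a minor phase 2 blinding statement is also not assured

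*Protocol*

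**What the plan says.** **Phase 3 consent.** Section 1.7.6 explains the conflict: "The lead researcher is also the clinical lead sonographer for the ultrasound service within the trust". It says this may produce conflict and bias. To avoid that and reduce the risk of coercion, "consent for participation within phase 3 of the study will be obtained by the recognised PhD clinical supervisor", a consultant urologist. Section 1.9.3 describes the leaflet and the face-to-face discussion, "where written consent will be obtained by the lead researcher", and adds a general assurance that care will be taken over the researcher's dual role. On numbers, section 1.7.4 states: "The phase 3 cohort will be a maximum of 12 staff members from varying professions".

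**Phase 2 consent meeting.** Section 1.6.6 states: "The lead researcher will be blinded to the results of the MRI and any previous ultrasound image collection at this time to minimise undue coercion". Section 1.6.2 invites phase 1 men managed by active surveillance or watchful waiting to continue into phase 2, up to 30 men. For phase 1, section 1.5.12 says that "the scores submitted on the data collection forms will be uploaded onto the database by the lead researcher". Section 1.5.13 then says that "the lead researcher will review the clinical information taken as part of the standard care consultation"; in the same step the PI-RADS score, lesion site and Gleason score enter the database. Section 1.5.14 has the lead researcher make the comparisons once each man's record is complete.

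**The concern.** The main issue is which instruction the site will follow. A team working from the consent chapter (1.9) would have the lead researcher take staff consent, which is the arrangement that 1.7.6 was written to avoid. The protocol treats the matter as serious: section 1.10.3.1 calls the lead researcher's leadership position the greatest phase 3 risk, and mentions staff who feel obliged to join or want to please. Phase 3 consent also covers more than a survey. Under 1.9.3 it includes performing the scans and scoring stored images. What is at stake is whether staff agree freely.

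The lesser issue is that 1.6.6 offers blinding as a protection against coercion of patients, while other sections give the same person the phase 1 results of some of those patients. If the blinding does not hold for continuing men, the protocol describes a safeguard that they may not have.

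**Working it through.** No formula applies, and the plan gives no figure to reproduce. The check sets the sections side by side.

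**Phase 3 consent**

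1. Section 1.7.6: the consent-taker is the PhD clinical supervisor, for the stated purpose of limiting coercion.
2. Section 1.9.3: the consent-taker is the lead researcher.
3. Both concern the consent of the same phase 3 staff. Neither section limits itself to one professional group or one stage of consent, so they cannot be read as covering different cases.
4. No other section reconciles them. Section 1.9 says only that consent will be written.
5. Ceiling: 12 staff (1.7.4), so at most 12 consents. The cohort in 1.7.4 includes radiologists, urology consultants and urology registrars as well as sonographers. The number of sonographers is not given, so the number of staff under the lead researcher's leadership cannot be derived.

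**Phase 2 consent meeting**

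1. Section 1.6.6 claims blinding to two things at the meeting: MRI results and earlier ultrasound.
2. Earlier ultrasound: 1.5.12 has the lead researcher upload the phase 1 scores.
3. MRI and histology: 1.5.13 names the lead researcher for the review of clinical information. It describes the MRI and histology entries without naming who makes them. Section 1.5.14 then names the lead researcher for the comparison of each completed record, which extends to MRI and histology.
4. Timing: comparison proceeds man by man as records are completed, and section 1.4.4 says the phases run concurrently. Nothing holds this work back until after a continuing man's phase 2 consent meeting, and nothing places it before that meeting.
5. The blinding therefore depends on an order of events that the protocol does not state. It is not assured, but it is not shown to fail for any given man.
6. Ceiling: the phase 2 cap is 30, so at most 30 consent meetings, and only those where the phase 1 data had already been handled.

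**The case against.** **On phase 3.** The lead researcher's consent role is not the only thing standing between staff and pressure. Section 1.7.6 gives a right to withdraw without adverse effects, 1.10.3.1 brings in an academic supervisory team that is not involved, 1.7.9 distributes the survey anonymously (while admitting the limits of that in a small group), and 1.14 promises supervision of phase 3 data collection and analysis. This stands. It would be wrong to call the separate consent-taker the sole protection. None of these measures settles who takes consent, however, so the contradiction remains.

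A reader might also infer that all 12 staff are exposed to pressure, or that survey answers would be less candid. The documents support neither. The conflict described is with the ultrasound service, and the cohort spans other professions. Section 1.7.5 has the lead researcher alone analyse the data whoever takes consent, so an effect of the consent-taker on candour is not shown.

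**On phase 2.** A tempting stronger reading is that the phase 2 scans or scores are themselves unblinded, so that comparison with baseline is biased, and that the lead researcher should be barred from scanning and scoring. Section 1.7.5 does say this person takes part in acquisition and scoring, with no phase excepted. But section 1.6 makes a separate statement: "The multi-parametric US examination will be performed blinded to the previous examinations and histology results". Section 1.5.9 brings in a randomly allocated sonographer, and 1.5.11 and 1.6.8 use two randomly allocated readers, with images that carry no patient identifiers. Part of the scan protocol (1.5.10) and the image review pathways in Appendices 4 and 5 are not shown in this copy and may separate the roles further. The number of phase 2 examinations affected may be zero. The documents do not support the stronger reading.

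**Conclusion.** The phase 3 contradiction is established on the face of the text: 1.7.6 and 1.9.3 name different consent-takers, and following 1.9.3 removes the one chosen to limit coercion. Its size is at most 12 consents. It bears on whether participation is voluntary, and no quantitative result is claimed to change. It should be corrected.

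The phase 2 point is secondary and minor. The 1.6.6 blinding statement is not assured for continuing men, at most 30. It concerns what the lead researcher knows at a consent meeting, and no bias in the ultrasound scores is claimed. It rests on the absence of any stated timing in the visible text. If the site in practice completes phase 1 records only after phase 2 consent, the statement would hold and would need only to say so.

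**What to change.** **Phase 3.** Amend 1.9.3 so that the PhD clinical supervisor obtains written consent, in agreement with 1.7.6. The cost is one sentence. The supervisor takes up to 12 consents, which 1.7.6 already plans.

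**Phase 2.** Choose one of two changes to 1.6.6. Either limit the blinding statement to men whose phase 1 data the lead researcher has not yet handled, which costs only wording; or have an existing colleague take phase 2 consent for continuing men, which costs at most 30 meetings.

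No change to who scans or scores is proposed. Excluding the lead researcher would cost a small team a trained reader. Doing so in phase 2 alone would also make the baseline and follow-up readers differ, for a problem that the visible text does not show to exist.
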